- A provider appointment to discuss additional therapeutic options for treatment of IC/PBS
- 2. Vital sign assessment including blood pressure
 - a. If blood pressure is elevated from baseline, will recommend patients repeat a blood pressure with the primary care provider; if they do not have a primary care provider, we will have them obtain a blood pressure check in 1 week.
- 3. Blood draw for study exit hepatic panel
 - a. Study participants will be called with the results of their post-study blood test results
- 4. Complete study questionnaires
 - a. Interstitial Cystitis Symptom Index

- b. Interstitial Cystitis Problem Index
- c. Pelvic pain and urgency/frequency patient symptom scale (PUF)
- d. Visual Analog Scale
- e. Medical Outcomes Study Short Form 36 (SF-36)
 - i. This will be scored prior to the participant leaving the office. In the event that they have low scores in areas assessing "role limitations due to emotional problems," (questions 17, 18, 19) "energy/fatigue" (23, 27, 29, 31) or "emotional wellbeing" (24, 25, 26, 28, 30), participants will be offered a referral to discuss any mental health concerns, if they desire.
- f. Study completion and tolerability survey
- 5. Return unused study medication
- 6. Provide two completed 24-hour bladder diaries
 - a. One performed prior to starting the medication
 - b. One performed at completion of the study last day
 - c. Participants will be given instructions about completing this on the last day of taking study medication, or the day after completion of all study.

Ethical and Regulatory considerations Regulatory document collection:

Patients will fill out the above mentioned forms prior to starting the study, then again at the conclusion of the study. Documents will be kept in a locked filling cabinet and only those individuals listed on the RI 8.1 delegation log will be able to access it. In addition, the information will be typed into spreadsheets and stored on the Collaboration Portal.

IRB review

IRB approval of the revised protocol including the comments and recommendation from the FDA will be submitted for review prior to initiation of enrollment.

Informed consent administration:

Potential study participants will be given the consent form to participate in this study prior to being asked to formally enroll by signing the consent form to allow for ample time to read the consent form and to discuss the study with family, other physicians and friends, if they so choose.

Study procedures

Patients who have been newly diagnosed with IC/PBS or those who have not received treatment in the past four weeks, who are interested in participating in the study and who meet inclusion, and who do not meet exclusion criteria will be given a consent form in the clinic or sent one by mail. Potential participants will be encouraged to discuss the study with family, a primary care physician, other physicians, and/or friends.

Once patients decide they would like to participate, they will make an appointment to return to the Center for Pelvic Health of the NorthShore University HealthSystem and meet with research personnel for:

- 1. Consent
- 2. Vital sign assessment including blood pressure
- 3. Completion of intake forms

- 4. Randomization
- 5. Blood collection
- 6. Urine pregnancy test if premenopausal
- 7. Distribution of study medication.
- 8. All patients will receive information about a bladder diet and bladder drills to assure patients are receiving treatment known to be beneficial in IC/PBS.

Prior to starting the study medication, patients will be asked to complete a 24-hour bladder diary.

The study medications will be listed in epic as "naltrexone/placebo" to inform other providers that the patient may be taking low-dose naltrexone as part of a research study. The study medication and placebo will be free of charge to patients, placing no additional financial burden on the patient or insurance company. The blood collection and hepatic panel will also be performed free of charge for study participants.

Participants will also be encouraged to contact research personnel with any questions or concerns at any point during the research study. If serum transaminases and bilirubin are elevated at the baseline blood test, study participants will be notified of their results, withdrawn from the study, and encouraged to follow up with their primary care provider.

Participants will be instructed to take one capsule nightly for two weeks, then increase their dosage to two capsules at night for four weeks. They will be given a log where they can record the date and time they take the medication.

After two weeks, participants will be contacted by research personnel by phone to check to see that they completed the 24-hour bladder diary, to make sure they are taking the medication, and to ask about any adverse effects from the study medication. If adverse effects are noted, study personnel will attempt to trouble shoot. For example, the most commonly reported adverse effect is vivid dreams. If study participants experience this, they will be encouraged to try taking the medication in the morning. If study participants have not completed the 24 bladder diary, they will be encouraged to do so as soon as possible.

At the completion of the six weeks, patients will return to the office for:

- A provider appointment to discuss additional therapeutic options for treatment of IC/PBS
- 2. Vital sign assessment including blood pressure
- 3. Blood collection for study exit hepatic panel
- 4. Complete study questionnaires
 - a. Interstitial Cystitis Symptom Index
 - b. Interstitial Cystitis Problem Index
 - c. Pelvic pain and urgency/frequency patient symptom scale (PUF)
 - d. Visual Analog Scale
 - e. Medical Outcomes Study Short Form 36 (SF-36)
 - f. Study completion and tolerability survey
- 5. Return unused study medication
- 6. Provide two completed 24-hour bladder diaries
 - a. One performed prior to starting the medication

- b. One performed at completion of the study last day
 - i. Participants will be given instructions about completing this on the last day of taking study medication, or the day after completion of all study
- 7. This concludes their participation in this research study

Study drug and comparator

Drug shipment/receipt: The medication will be compounded by Keefer's pharmacy into 2mg capsules. The medication will be shipped to the Skokie inpatient pharmacy.

Drug packaging: Keefer's pharmacy will be asked to supply 1,540 capsules of the study medication and placebo, which is enough for twenty-two study participants. Seventy capsules of medication and identical placebo will be placed into separate but identical moisture tight and light-resistant amber vials by the NorthShore pharmacy with specific lot numbers and expiration dates as determined by Keefer's pharmacy.

Drug storage: The medication will be stored at the NorthShore Skokie inpatient pharmacy in tight, light-resistant containers. The Beyond-Use-Date (BUD) for this nonaqueous formulation of low-dose naltrexone HCl capsules will be labeled as six months.

Drug preparation: The LDN study medication and placebo will be compounded and prepared by Keefer's pharmacy.

Drug dispensing and accountability: The medication will be dispensed by the Skokie NorthShore pharmacy to the research personnel to provide to the participant. Participants will return their pill vial, including any unused medication at the time of their six-week follow up visit. Any residual medication will be documented, and the medication returned to the pharmacy for disposal by onsite destruction.

Drug administration: the patients will take their appropriate randomized medication for a total of six weeks. The first two weeks, patients will take one capsule at night, and for the last four weeks, they will take two capsules at night.

Contraindications/concomitant medications: Absolute contraindications to taking LDN include pregnancy, moderate-severe alcohol use disorder, and opioid dependence. In the case reports and small randomized trials, LDN does not appear to interfere with other medications patients were taking at the time of the study.

Breaking the blind: In the event of an adverse event, a phone call can be made to the NorthShore Skokie inpatient pharmacy to determine if they are taking the study medication or placebo. If this should occur, the phone call should be followed up with written documentation in the form of an email with notification of the break in the blind.

Drug destruction: Study participants will be requested to return the pill vials to clinic. Any residual medication will be documented, and the medication returned to the pharmacy for disposal by onsite destruction.

Medication compliance assessment: Study participants will be requested to return the pill vials to clinic. Any residual medication will be documented, and the medication returned to the

pharmacy for disposal by onsite destruction. Participants will also be asked to keep a log of when they take their medication.

Safety Assessment

Adverse Experiences (AEs): Study participants will be asked to document any adverse experiences or events they experience while participating in the study. The National Cancer Institute Common Terminology Criteria for Adverse Events (CTCAE) version 5.0 will be used for adverse event reporting. The CTCAE describes an adverse event as "any unfavorable and unintended sign, symptom, or disease temporally associated with the use of a medical treatment or procedure that may or may not be considered related to the medical treatment or procedure."

Documentation of AEs: All AEs experienced by study participants will be documented in the collaboration portal.

Coding of AEs: AEs will be given a grade according to the CTCAE version 5.0

Serious Adverse Events

Definition: Serious AEs will be given a grade according to the CTCAE version 5.0

Reporting: Serious AEs will be documented in writing

Expected AEs/toxicities: To date, there are no reports of interactions between LDN and other medications. The sample size of these studies is small, and there are likely a large number of interactions that have yet to be tested (39). Other trials have reported vivid dreams (34), nausea, epigastric pain, mood alteration, mild irritability, headache, and joint pain. (43)

Unplanned visits: Study participants will be encouraged to contact research personnel with any questions or concerns they have about the medication or the study. If study personnel determine the patient needs a clinic visit, the patient will be seen by a provider, and that visit will be documented in Epic as a medical visit. The visit will also be included in the patient's research documentation.

Subject Completion and Early Withdrawal Procedures for completion

Upon completion of the six-week study period, participants will have an appointment with their physician to discuss additional treatment options for IC/PBS. At that visit, study participants will complete study forms and submit two 24-hour bladder diaries, and have a blood sample collected. They will receive \$50 in compensation. In the event that study participants are unable to complete the study, they will receive a prorated compensation of \$20 in the form of a gift card.

Procedures for early withdrawals:

Patients will be free to withdrawal for any reason or if deemed necessary by research staff or any other medical provider.

Reasons for withdrawals:

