IC PalN Trial: Interstitial Cystitis Pain Improvement with Naltrexone; The effect of low-dose naltrexone on symptoms and pain of patients with interstitial cystitis/painful bladder syndrome: a randomized placebo-controlled prospective trial.

August 18, 2021 Version 4

Principal Investigator: [name] MPH

Co-Principal Investigator: [name] MPH

ClinicalTrials.Gov: NCT04313972

IND: 155667

Background and Significance

Interstitial cystitis/painful bladder syndrome (IC/PBS) is a debilitating condition characterized by urinary urgency, frequency, nocturia, and pain, without evidence of urinary tract infection or other identifiable causes (1, 2, 6). This debilitating disorder gravely impacts affected patients' quality of life, and about 2.7-6.5% of US women have bladder symptoms consistent with IC/PBS. (1). IC/PBS is a diagnosis of exclusion, and more invasive testing, such as cystoscopy should only be considered when the diagnosis is not straightforward, as the only consistent cystoscopic finding that leads to the diagnosis of IC/BPS is the appearance of inflammatory lesions or ulcerations, termed Hunner's ulcers; these are only seen in about 15% of patients diagnosed with IC/PBS(7). Glomerulations (pinpoint petechial hemorrhages) may also be seen, but can also be present in healthy patients (17).

IC/PBS often coexists with other chronic pain syndromes, such as irritable bowel syndrome, chronic fatigue syndrome, and fibromyalgia (5). Studies suggest there may be a common pathogenic mechanism, such as abnormalities in autonomic function and in visceral nociception (3, 4). The exact etiology of IC/BPS is unknown, but several hypotheses have been proposed. These include dysfunction of the superficial layer of the extracellular matrix of the glycosaminoglycan (GAG) layer, downregulation of tight junction proteins, increased urothelial permeability, mast cell activation, neurogenic inflammation, and psychosomatic factors (13)

Treatment of IC/PBS remains challenging as the etiology of the disorder remains unclear, symptoms vary across patients, and there are few high-quality trials evaluating the efficacy and safety of treatment options. As such, many treatments exist (7), and they are generally limited to symptom relief (6). In 2011, the American Urologic Association proposed a six-stage treatment algorithm (8). First-line therapies include conservative behavioral interventions such as a bladder diet and timed voiding or bladder drills.

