- c. The change in number of patient voids during at night when comparing LDN against placebo as determined from 24 hour bladder diary performed by patient prior to initiating treatment, and at the conclusion of 6 weeks of treatment.
- d. The decrease is pelvic pain and urgency/frequency symptoms
- e. The decrease in pelvic pain and urgency/frequency bother
- f. Patient perceived changes in quality of life as measured by the medical outcomes study short form 36 (SF-36)
- g. The percentage of patients complaining of adverse effects from LDN including vivid dreams, nightmares, insomnia, GI disturbances such as stomach cramps or diarrhea, agitation, anxiety, flu-like symptoms and headaches. A check list of these symptoms will be provided at the follow up visit.
- h. Patient tolerability of LDN using a tolerability survey, as well as instructing the patient to return any remaining medication at the end of the 6 week study period.
- i. The decrease in use of pain medications while using LDN as determined by a pain medication diary

Study Design

This will be a randomized double-blinded placebo-controlled prospective trial performed by the Center for Pelvic Health at the NorthShore University HealthSystem to determine the effect of using low-dose naltrexone on symptoms of patients with interstitial cystitis/painful bladder syndrome. Patients meeting diagnostic criteria for IC/PBS by AUA guidelines will be eligible to participate. A patient must then meet all applicable inclusion and exclusion criteria.

Primary endpoints

- 1. Effect of LDN in decreasing symptoms associated with IC/PBS
- 2. Decrease in pain symptoms associated with IC/PBS

Secondary endpoints

- 1. Decrease in IC/PBS associated problems
- 2. Decrease in number of patient voids during the day
- 3. Decrease in number of patient voids at night
- 4. The decrease is pelvic pain and urgency/frequency symptoms
- 5. The decrease in pelvic pain and urgency/frequency bother
- 6. Changes in quality of life
- 7. Patient tolerability of LDN
- 8. Adverse effects/reactions of LDN
- 9. Decrease adjuvant pain medication use while taking LDN

Number and Definition of Arms

There will be two study arms

- Study medication arm: The first arm will receive LDN one 2mg capsule at night for two
 weeks, followed by two 2mg capsules (total of 4mg) for the remaining four weeks of the
 study.
- Placebo arm: The second arm will receive the placebo for six weeks, and will take 1

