Consent will be obtained in clinic by research personnel, after study participants have had ample time to discuss the study with family, a primary care physician, other physicians, and/or friends. They will make an appointment with research personnel at a convenient time for the study participant.

Enrollment

After signing the consent form, participants will be given a study identification number (ID). This ID will not be linked to their medical record. There will be a master sheet kept in a locked filing cabinet at the Center for Pelvic Health at the Skokie Ambulatory Care Center. Only those study personnel on the R8.1 delegation log will be able to access this master sheet. The participant's name and study ID will also be typed into a spreadsheet and stored on the Collaboration Portal, and access will only be given to [name].

Baseline Evaluation

Study participants will be asked to answer demographic information including:

- 1. Age
- 2. BMI
- 3. Menopausal status
 - a. If premenopausal, type of contraception
- 4. Tobacco use
- 5. Marijuana use
- 6. Pain medication use in the last month
- 7. Prior medical and surgical history, including medications and allergies
- 8. Length of time they have been experiencing symptoms of IC/PBS
- 9. Specific symptoms they are experiencing

Along with the following validated questionnaires:

- 1. Interstitial Cystitis Symptom Index
- 2. Interstitial Cystitis Problem Index
- 3. Pelvic pain and urgency/frequency patient symptom scale (PUF)
- 4. Visual Analog Scale
- 5. Medical Outcomes Study Short Form 36 (SF-36)
 - a. This will be scored prior to the participant leaving the office. In the event that they have low scores in areas assessing "role limitations due to emotional problems," (questions 17, 18, 19) "energy/fatigue" (23, 27, 29, 31) or "emotional well being" (24, 25, 26, 28, 30), participants will be offered a referral to discuss any mental health concerns, if they desire.

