At the enrollment appointment, vital signs will be obtained, including blood pressure. If participants are premenopausal, they will be asked to undergo a urine pregnancy test. Patients will be given a lab requisition form for a hepatic panel at the time of enrollment for a blood draw to evaluate serum transaminases and bilirubin. Once participants have their blood draw, they will be given and instructed to take one capsule nightly for two weeks, then increase their dosage to two capsules at night for four weeks. They will be given a log where they can record the date and time they take the medication, along with space for any additional notes they wish to share. Prior to starting the study medication, patients will be asked to complete a 24-hour bladder diary. They will also be instructed not to start the study medication until their blood work results with normal liver function. Participants will be called with the results of their blood work.

Treatment Schedule

Participants will be given a prescription bottle with 70 capsules. For the first two weeks, participants will take 1 capsule at night. After two weeks, they will take two capsules at night. Participants will be given a log to record taking the medication.

All patients will receive information about a bladder diet and bladder drills to assure patients are receiving treatment known to be beneficial in IC/PBS.

Follow-up Schedule

If serum transaminases and bilirubin are elevated at the baseline blood test, study participants will be notified of their results, withdrawn from the study, and encouraged to follow up with their primary care provider.

After two weeks, participants will be contacted by research personnel to check to see that they completed the bladder diary, to make sure they are taking the medication, and to ask about any adverse effects from the study medication. If adverse effects are noted, study personnel will attempt to trouble shoot. For example, the most commonly reported adverse effect in previous trials is vivid dreams. If study participants experience this, they will be encouraged to try taking the medication in the morning. If study participants have not completed the 24 bladder diary, they will be encouraged to do so as soon as possible.

Participants will also be encouraged to call prior to this two week check in telephone call with any questions or concerns that arise.

At the completion of the six weeks, patients will return to the office for:

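### The adverse-effect checklist is scheduled only at week 6, with no baseline and no rule for new or worsened symptoms, so pre-existing complaints may be counted and may dilute the comparison

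*Combined protocol and SAP*

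**What the plan says.** Outcome measures, item 2.g, defines the outcome as "The percentage of patients complaining of adverse effects from LDN including vivid dreams, nightmares, insomnia, GI disturbances such as stomach cramps or diarrhea", and goes on to agitation, anxiety, flu-like symptoms and headaches. The instrument follows: "A check list of these symptoms will be provided at the follow up visit". The follow-up visit is the return visit at the end of six weeks.

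Baseline Evaluation lists demographics, the two interstitial cystitis indices, the PUF scale, the pain scale and the SF-36. Two of its items come near the point: "Prior medical and surgical history, including medications and allergies" and "Specific symptoms they are experiencing". The second directly follows the item on how long the patient has had IC/PBS symptoms, and its scope is not defined. The enrollment steps there and under Study procedures add vital signs, a blood draw, a pregnancy test and a bladder diary, but no adverse-symptom checklist.

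Adverse effects are also sought in two other ways. Staff telephone at two weeks, among other things "to ask about any adverse effects from the study medication" (Follow-up Schedule; repeated in Study procedures). Under Safety Assessment, "Study participants will be asked to document any adverse experiences or events they experience while participating in the study".

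Safety Assessment adopts the CTCAE version 5.0 definition and grades, and Data Analysis compares the incidence and type of adverse events between arms. Neither section says how a symptom present before the first dose is handled.

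**The concern.** The listed symptoms are common, and this population is likely to bring some of them into the trial. Background and Significance states: "IC/PBS often coexists with other chronic pain syndromes, such as irritable bowel syndrome, chronic fatigue syndrome, and fibromyalgia". It also names nocturia as a feature of the disease. None of those three comorbidities is named as an exclusion. Users of sleep aids are excluded, but patients with untreated insomnia are not. The summary of earlier studies gives a precedent: in a fibromyalgia pilot, two of eight women had adverse effects traced to conditions they already had.

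With a single checklist at week 6 and no rule, a patient with long-standing diarrhea or poor sleep can be counted in either arm. Two things are then at stake. The raw percentage, which is the outcome as worded, mixes prevalence with effect and cannot be read as an adverse-effect rate. And if LDN does cause such symptoms, the contrast with placebo is attenuated. Identifying adverse reactions is one of the trial's specific aims. The plan takes a baseline for its questionnaires and bladder diaries but not for this measure.

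**Working it through.** **The plan's own figure.** The documents give no sample size or power for the adverse-effect outcome. The 22 per arm comes from Sample Size and concerns pain. It cannot be reproduced because no standard deviation or responder rates are stated. It is used here only as the number of patients available.

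**Inputs**
- n = 22 per arm (Sample Size). No dropout is applied.
- New-onset rate on LDN, p_L = 37%. This is the vivid-dreams rate in the fibromyalgia crossover study described in the background, borrowed as an illustration.
- New-onset rate on placebo, p_P = 10%. Assumption; 5% and 15% are also tried.
- Share with the symptom at baseline, b = 0, 20%, 30%, 50%. Assumption; the documents give no prevalence.
- Two-sided alpha 0.05. The level is in Data Analysis; two-sidedness is assumed.

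**Model.** If every baseline symptom persists and is ticked, the observed rate in an arm is b + (1 − b)p. The observed difference is therefore (1 − b)(p_L − p_P): the true difference shrinks by exactly the share b.

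**Power.** Φ[(d − 1.96·SE0)/SE1], where d is the difference, m is the mean of the two rates, SE0 = √(2m(1 − m)/n) and SE1 = √(p1(1 − p1)/n + p2(1 − p2)/n).

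**Worked case, b = 30%**
- LDN: 0.30 + 0.70 × 0.37 = 0.559. Placebo: 0.30 + 0.70 × 0.10 = 0.370. Difference 0.189.
- SE0 = 0.1504, SE1 = 0.1477; (0.189 − 1.96 × 0.1504)/0.1477 = −0.716; power 24%.
- Counting only new onset among symptom-free patients: 22 × 0.70 = 15.4 per arm, difference 0.27, SE0 = 0.1528, SE1 = 0.1448; (0.27 − 1.96 × 0.1528)/0.1448 = −0.204; power 42%.

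| Baseline share b | LDN v placebo, week 6 only | Difference (points) | Power, week 6 only | At risk per arm | Power, new onset only |
|---|---|---|---|---|---|
| 0% | 37.0% v 10.0% | 27.0 | 56% | 22 | 56% |
| 20% | 49.6% v 28.0% | 21.6 | 31% | 17.6 | 47% |
| 30% | 55.9% v 37.0% | 18.9 | 24% | 15.4 | 42% |
| 50% | 68.5% v 55.0% | 13.5 | 15% | 11 | 31% |

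Fisher's exact test gives lower week-6-only power: 46%, 21%, 15% and 9% down the rows.

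**Other placebo rates, b = 0 against b = 30%.** With 5% on placebo, the difference falls from 32.0 to 22.4 points and power from 76% to 32%. With 15%, it falls from 22.0 to 15.4 points and power from 38% to 17%.

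**The case against.** - **The form is not shown.** The outcome is worded as effects from LDN, and the checklist might ask about onset since starting the capsules. It is therefore not established that pre-existing symptoms will be counted, only that no stated rule prevents it. Without a baseline, onset would rest on six-week recall, or on blinded patients judging cause.
- **Other sources exist.** The week-2 call, the participants' own record, the medication log with its space for notes, and the medical history could date some symptoms. That is partial mitigation. None of them lists the checklist symptoms before dosing, and none is tied to 2.g.
- **Randomization balances baseline symptoms on average.** This stands: if LDN has no effect on these symptoms, no bias between arms is expected.
- **A reader might infer that the design makes LDN look safer than it is.** The documents do not support that as a general statement. The between-arm difference shrinks, but the LDN percentage itself rises (37.0% to 55.9% at b = 30%), which makes LDN look worse. Both arms are inflated, not only placebo.
- **A reader might infer that a baseline restores 56% power.** It does not, because fewer patients remain at risk; the last column of the table is the fair comparison. The trial was not sized for this outcome in any case.
- **A reader might infer that the checklist omits most of the expected effects.** Expected AEs/toxicities names "nausea, epigastric pain, mood alteration, mild irritability, headache, and joint pain" among others. But the open-ended gastrointestinal wording in 2.g can cover nausea and epigastric pain, headache is listed, and agitation and anxiety overlap with mood change. Joint pain is the clear gap in that list.

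**Conclusion.** The point holds as a measurement weakness in a secondary outcome. The checklist has one scheduled time point, no baseline, and no rule separating pre-existing from new or worsened symptoms. Pre-existing complaints may therefore be counted.

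The direction of attenuation follows from the model whenever LDN truly causes symptoms. Its size does not come from the documents. It depends on an assumed baseline prevalence, an assumed placebo rate, a 37% rate that belongs to vivid dreams (for which the documents give no reason to expect a high baseline prevalence), and the premise that baseline symptoms persist and are ticked. At an assumed 30% prevalence, the plan as written gives 24% power where new-onset counting gives about 42%. Severity is low: a worthwhile improvement, not a threat to the primary outcomes.

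**What to change.** 1. Give the same checklist at the enrollment visit, with the other questionnaires, and again at week 6. Participants are told to wait for their liver results before starting capsules, so a form completed at enrollment precedes the first dose.
2. Record presence and severity of each item. Define 2.g as the percentage of patients in each arm with a symptom new or worse than baseline. Including worsening keeps patients who already had the symptom in the analysis.
3. Add expected effects that the wording of 2.g does not clearly cover: for example joint pain (Expected AEs/toxicities), and yawning, dry mouth and thirst (Evaluation of benefits, risks and discomforts).

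The cost is one page at an existing visit, a few extra minutes per participant, and a sentence in Data Analysis.
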